7.3 LOST TO FOLLOW-UP

N/A

8 STUDY ASSESSMENTS AND PROCEDURES

8.1 EFFICACY ASSESSMENTS

Participant outcomes will be reminded before starting fasting (day 1) and the end of fasting (day 2) via telephone calls, text message and/or email.

Questionnaires will be self-administered through HIPAA compliant E-platform CRIQ.

Procedure List:

- Screening (SCR): study explanation, informed consent, medical history, and instructions.
- Day 1
 - finish dinner by 5 pm followed by water-only fasting;
- Day 2
 - Continue the water-only fast, consume a breakfast or a Fast Bar™.

Examination and tests will include:

- Fingerstick for blood glucose and ketone (BHB) before breakfast on day 1;
- Fingerstick for blood glucose and ketone (BHB) on baseline timepoint (before breakfast), and 1, 2, 3, and 4 hours after consuming the breakfast bar or the Fast Bar™;
- Questionnaires and Surveys:
 - Nurse's Health Survey 2016 [9-11]: to evaluate medical history, newly developed conditions, changes in health conditions and healthcare utilization/medications;
 - Food evaluation;
 - Self-evaluation;

8.2 SAFETY AND OTHER ASSESSMENTS

N/A

8.3 ADVERSE EVENTS AND SERIOUS ADVERSE EVENTS

8.3.1 DEFINITION OF ADVERSE EVENTS (AE)

Adverse event means any untoward medical occurrence associated with the use of an intervention in humans, whether or not considered intervention-related (21 CFR 312.32 (a))

8.3.2 DEFINITION OF SERIOUS ADVERSE EVENTS (SAE)

An adverse event (AE) or suspected adverse reaction is considered "serious" if, in the view of either the investigator or sponsor, it results in any of the following outcomes: death, a life-threatening adverse event, inpatient hospitalization or prolongation of existing hospitalization, a persistent or significant incapacity or substantial disruption of the ability to conduct normal life functions. Important medical events that may not result in death, be life-threatening, or require hospitalization may be considered serious when, based upon appropriate medical judgment, they may jeopardize the participant and may require medical or surgical intervention to prevent one of the outcomes listed in this definition. Examples of such medical events include allergic bronchospasm requiring intensive treatment in an emergency room or at home, blood dyscrasias or convulsions that do not result in inpatient hospitalization, or the development of drug dependency or drug abuse.

8.3.3 CLASSIFICATION OF AN ADVERSE EVENT

8.3.3.1 SEVERITY OF EVENT

For adverse events (AEs) not included in the protocol defined grading system, the following guidelines will be used to describe severity.

- **Mild** – Events require minimal or no treatment and do not interfere with the participant's daily activities.
- **Moderate** – Events result in a low level of inconvenience or concern with the therapeutic measures. Moderate events may cause some interference with functioning.
- **Severe** – Events interrupt a participant's usual daily activity and may require systemic drug therapy or other treatment. Severe events are usually incapacitating. Of note, the term "severe" does not necessarily equate to "serious".
- **Extreme** – life-threatening or disabling

8.3.3.2 RELATIONSHIP TO STUDY INTERVENTION

All adverse events (AEs) must have their relationship to study intervention assessed by the clinician who examines and evaluates the participant based on temporal relationship and his/her clinical judgment. The degree of certainty about causality will be graded using the categories below. In a clinical trial, the study product must always be suspect.

- **Related** – The AE is known to occur with the study intervention, there is a reasonable possibility that the study intervention caused the AE, or there is a temporal relationship between the study intervention and event. Reasonable possibility means that there is evidence to suggest a causal relationship between the study intervention and the AE.

- **Not Related** – There is not a reasonable possibility that the administration of the study intervention caused the event, there is no temporal relationship between the study intervention and event onset, or an alternate etiology has been established.

8.3.3.3 EXPECTEDNESS

[name], will be responsible for determining whether an adverse event (AE) is expected or unexpected. An AE will be considered unexpected if the nature, severity, or frequency of the event is not consistent with the risk information previously described for the study intervention.

8.3.4 TIME PERIOD AND FREQUENCY FOR EVENT ASSESSMENT AND FOLLOW-UP

The occurrence of an adverse event (AE) or serious adverse event (SAE) may come to the attention of study personnel during study or upon review by a study personnel.

All AEs including local and systemic reactions not meeting the criteria for SAEs will be captured on the appropriate case report form (CRF). Information to be collected includes event description, time of onset, clinician's assessment of severity, relationship to study product (assessed only by those with the training and authority to make a diagnosis), and time of resolution/stabilization of the event. All AEs occurring while on study must be documented appropriately regardless of relationship. All AEs will be followed to adequate resolution.

Any medical condition that is present at the time that the participant is screened will be considered as baseline and not reported as an AE. However, if the study participant's condition deteriorates at any time during the study, it will be recorded as an AE.

Changes in the severity of an AE will be documented to allow an assessment of the duration of the event at each level of severity to be performed. AEs characterized as intermittent require documentation of onset and duration of each episode.

[name], MS, RDN, will record all reportable events with start dates occurring any time after informed consent is obtained until the last day of study participation. Events will be followed for outcome information until resolution or stabilization.

8.3.5 ADVERSE EVENT REPORTING

Following adverse event (AE) or serious suspected adverse reaction will be reported to IRB within 10 working days after investigators becoming aware of the event.

8.3.6 SERIOUS ADVERSE EVENT REPORTING

Following serious adverse event (SAE) or serious suspected adverse reaction will be reported to IRB within 10 working days after investigators becoming aware of the event.

8.3.7 REPORTING EVENTS TO PARTICIPANTS

[name], MS, RDN, will report eventual AE and/or SAE to the participant. Any adverse effects will be reported to participant directly in person or via phone/video conference/email.

8.3.8 EVENTS OF SPECIAL INTEREST

N/A

8.3.9 REPORTING OF PREGNANCY

N/A

8.3.10 DEFINITION OF UNANTICIPATED PROBLEMS (UP)

The Office for Human Research Protections (OHRP) considers unanticipated problems involving risks to participants or others to include, in general, any incident, experience, or outcome that meets all of the following criteria:

- Unexpected in terms of nature, severity, or frequency given (a) the research procedures that are described in the protocol-related documents, such as the Institutional Review Board (IRB)-approved research protocol and informed consent document; and (b) the characteristics of the participant population being studied;
- Related or possibly related to participation in the research (“possibly related” means there is a reasonable possibility that the incident, experience, or outcome may have been caused by the procedures involved in the research); and
- Suggests that the research places participants or others at a greater risk of harm (including physical, psychological, economic, or social harm) than was previously known or recognized.

8.3.11 UNANTICIPATED PROBLEM REPORTING

The investigator will report unanticipated problems (UPs) to the reviewing Institutional Review Board (IRB). The UP report will include the following information:

- Protocol identifying information: protocol title and number, PI's name, and the IRB project number;
- A detailed description of the event, incident, experience, or outcome;
- An explanation of the basis for determining that the event, incident, experience, or outcome represents an UP;
- A description of any changes to the protocol or other corrective actions that have been taken or are proposed in response to the UP.

8.3.12 REPORTING UNANTICIPATED PROBLEMS TO PARTICIPANTS

[name], MS, RDN, will report eventual UPs to the participant. Any adverse effects will be reported to participant directly in person, via phone or Zoom.

9 STATISTICAL CONSIDERATIONS

9.1 STATISTICAL HYPOTHESES

The primary trial outcome will be the ketone (beta-hydroxybutyrate, BHB) levels 3 hours (T3) after consuming the Fast and changes in BHB area under the curve (AUC) between 0 to 4 hours after consuming the study foods on day2.

We hypothesize that the breakfast bar group will show significant lower blood BHB level compared to the Fast Bar group.

9.2 SAMPLE SIZE DETERMINATION

Sample-size estimation is based on two considerations:

1. Sample-size estimation is based on pilot studies assuming ketone (BHB) levels of 0.25 (SD: 0.19) and 0.16 (SD: 0.05) mM for the Fast Bar and the Breakfast groups, respectively. With t test (one-

tailed) of difference between two independent means, a total sample size of 62 will be necessary to achieve 80% power with an α error probability of 0.05. Sample size calculation was performed using the GPower v3.1.9.6 (Franz Faul, University Kiel, Germany; Actual power = 0.8164386; Actual α = 0.0291400).*

2. Sample-size estimation is based on Fisher's exact test (one tailed) for proportion difference between the breakfast and Fast Bar groups: food consumption will reduce blood ketone in 67% vs. 33% of the participants in the breakfast and Fast Bar groups, respectively. A total sample size of 64 will be necessary to achieve 80% power with an α error probability of 0.05. **

Based on prior experience in similar dietary intervention studies, we anticipate an approximate 10% dropout and/or data loss. 36 subjects per group will be enrolled. Sample size calculation was performed using the GPower v3.1.9.6 (Franz Faul, University Kiel, Germany; Actual power = 0.8164386; Actual α = 0.0291400). A fasting only group (32 subjects) will also be included for comparison. A total 108 subjects will be enrolled.

* **t tests** – Means: Difference between two independent means (two groups)

Analysis: A priori: Compute required sample size

Input:	Tail(s)	= One
	Effect size d	= 0.6478342
	α err prob	= 0.05
	Power (1- β err prob)	= 0.8
	Allocation ratio N2/N1	= 1
Output:	Noncentrality parameter δ	= 2.5505258
	Critical t	= 1.6706489
	Df	= 60
	Sample size group 1	= 31
	Sample size group 2	= 31
	Total sample size	= 62
	Actual power	= 0.8096862

** **Exact** – Proportions: Inequality, two independent groups (Fisher's exact test)

Options: Exact distribution

Analysis: A priori: Compute required sample size

Input:	Tail(s)	= One
	Proportion p1	= 0.67
	Proportion p2	= 0.33
	α err prob	= 0.05
	Power (1- β err prob)	= 0.8
	Allocation ratio N2/N1	= 1
Output:	Sample size group 1	= 32
	Sample size group 2	= 32
	Total sample size	= 64
	Actual power	= 0.8164386
	Actual α	= 0.0291400

9.3 POPULATIONS FOR ANALYSES

All participants will be included in the intention-to-treat analyses of the results. Participants who are removed from study for non-compliance or for safety reasons will still have their data included in the final analysis, unless they withdraw consent to have their data included, and will not be replaced.

9.4 STATISTICAL ANALYSES

9.4.1 GENERAL APPROACH

Continuous trial outcome variables will be evaluated for normality; normalizing transformations or nonparametric statistics will be used as needed. All group comparisons on post-randomization efficacy outcomes will include randomized treatment (Fast Bar vs breakfast). A 1-sided level of significance set at $P<0.05$ will be used for the primary outcome; secondary and exploratory outcomes will not be adjusted for multiple hypothesis testing.

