9.4.2 ANALYSIS OF THE PRIMARY EFFICACY ENDPOINT(S)

The primary trial outcome will be the ketone (beta-hydroxybutyrate, BHB) levels 3 hours (T3) after consuming the study foods (Breakfast Bar or Fast Bar) and changes in BHB area under the curve (AUC) between 0 to 4 hours after consuming the study foods on day2.

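### No test is named for either primary BHB measure, and an unspecified normality check may choose it, so the power in 9.2 is tied to no fixed primary analysis; two figures in 9.2 also need correcting

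*Combined protocol and SAP*

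**What the plan says.** Section 9.1 gives the direction of the effect: "We hypothesize that the breakfast bar group will show significant lower blood BHB level compared to the Fast Bar group". Section 9.4.2 lists the primary measures as BHB at T3 and "changes in BHB area under the curve (AUC) between 0 to 4 hours after consuming the study foods on day2", and stops there. Section 9.4.1 identifies the treatment contrast as Fast Bar against breakfast and sets a one-sided 0.05 level for the primary outcome, in the singular. On the choice of method it says only: "Continuous trial outcome variables will be evaluated for normality; normalizing transformations or nonparametric statistics will be used as needed".

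Section 9.2 sizes the trial in two ways:

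- A one-tailed t-test assuming "ketone (BHB) levels of 0.25 (SD: 0.19) and 0.16 (SD: 0.05) mM for the Fast Bar and the Breakfast groups", for which "a total sample size of 62 will be necessary to achieve 80% power".
- A one-tailed Fisher's exact test assuming "food consumption will reduce blood ketone in 67% vs. 33% of the participants in the breakfast and Fast Bar groups, respectively", for which "A total sample size of 64 will be necessary to achieve 80% power".

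It then says "we anticipate an approximate 10% dropout and/or data loss. 36 subjects per group will be enrolled". It adds a fasting-only group of 32 and a total of 108. Section 6.3 describes 12 blocks of 9 at 1:1:1.

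**The concern.** The contrast is stated, but the test and the scale are not. A raw-mean comparison, a log-scale comparison and a rank test address different quantities, and 9.4.1 lets a look at the outcome data move the primary analysis from one to another. The t-test calculation in 9.2 covers only the raw-mean version.

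The Fisher power does not depend on normality, but it concerns the proportion of participants whose ketone falls. Neither 9.1 nor 9.4.2 names that as an endpoint. Within 9.4, Fisher's test is named only for adverse events (9.4.4). The one possible home for the proportion is a generic secondary line in 9.4.3 on the prevalence of categorical outcomes. Change in AUC has no SD and no power calculation at all.

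So neither stated power belongs to a named primary test, and a reader of the results could not tell whether the reported primary analysis was the planned one.

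**Working it through.** **1. Reproduce the t-test figure (inputs from 9.2).** Difference 0.25 - 0.16 = 0.09 mM. Root-mean-square SD = sqrt((0.19² + 0.05²)/2) = 0.1389. d = 0.09/0.1389 = 0.6478. At 31 per arm: noncentrality 2.5505, df 60, critical t 1.6706, power 0.8097. This matches the output block (0.8096862). At 30 per arm power is 0.798, so 31 is the minimum.

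**2. Reproduce the Fisher figure.** Full enumeration at 32 per arm, 0.67 vs 0.33, one-sided 0.05: power 0.8164, actual alpha 0.0291. Both match. At 31 per arm power is 0.796.

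**3. Which calculation sets enrolment.** 64/0.9 = 71.1, so 36 per arm; 62/0.9 = 68.9, so 35 per arm. Fisher sets the 36. Conversely, 36 × 0.9 = 32.4, or about 32 evaluable per arm.

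**4. Two figures in 9.2.** The t-test paragraph prints power 0.8164386 and alpha 0.0291400. Those are the Fisher outputs; the t-test block gives 0.8096862 at alpha 0.05. Also, 36 + 36 + 32 = 104, whereas 12 × 9 = 3 × 36 = 108.

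**5. Is a switch plausible for T3 BHB?** The Fast Bar SD is 0.19/0.25 = 76% of the mean, on a variable that cannot be negative. A symmetric, single-peaked variable with a zero floor has SD at most 1/sqrt(3) = 58% of its mean (the uniform case; 0.144 mM at a mean of 0.25). The pilot values are sample estimates, so this suggests skew without proving it. If the truth were uniform from zero, a sample ratio of at least 0.76 would still occur in 23% of pilots with n = 4, 19% with n = 6, 12% with n = 10 and 4% with n = 20. The pilot's n, time point and shape are not given. The argument does not extend to change in AUC, which can be negative.

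**6. Power if the analysis switches.** Simulated at 32 evaluable per arm, one-sided 0.05, with the means and SDs of 9.2. Shape and floor are assumptions.

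| Shape | Floor (mM) | Welch | Log scale | Rank-sum |
|---|---|---|---|---|
| Lognormal | 0 | 0.91 | 0.64 | 0.62 |
| Lognormal | 0.05 | 0.93 | 0.84 | 0.71 |
| Lognormal | 0.08 | 0.95 | 0.93 | 0.83 |
| Lognormal | 0.10 | 0.96 | 0.97 | 0.94 |
| Gamma | 0 | 0.87 | 0.31 | 0.49 |
| Gamma | 0.05 | 0.89 | 0.55 | 0.46 |
| Gamma | 0.08 | 0.90 | 0.71 | 0.45 |
| Gamma | 0.10 | 0.92 | 0.82 | 0.49 |
| Normal (floor ignored) | none | 0.82 | not applicable | 0.78 |

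**7. Welch on the inputs of 9.2 (normal theory).** Power is 0.804 at 31 per arm (df about 34) and 0.815 at 32, slightly below the pooled t-test (0.810 and 0.821).

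**8. If alpha were split equally over two primary measures (0.025 one-sided each).** Pooled t-test power is 0.72 at 32 per arm and 0.77 at 36.

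**The case against.** The strongest reply is that the plan's rule is conditional, so always-log and always-rank figures do not describe it, and that its error rate may be sound. One version was simulated: Shapiro-Wilk at 5% in each arm, with or without a log step, then rank-sum, at 32 per arm with both arms identically distributed. It rejected in 0.045-0.057 of trials, so there was no material inflation under that null. A reader might infer that choosing a test from the data inflates type I error here; neither the documents nor this check supports that. The same rule did have low power in the zero-floor shapes (0.47-0.65) and in gamma with a 0.10 floor (0.49), but not in lognormal with a 0.10 floor (0.93-0.94). What stands is uncertainty about power, not a demonstrated loss.

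Three further replies have merit. The generic line in 9.4.3 could house the ketone-reduction proportion as a secondary outcome, so it is too strong to say that proportion has no possible place in 9.4. The fasting group's 32 may mean evaluable participants, which would fit 36 enrolled and 108 in total; on that reading the text needs clarifying and the arithmetic is right. And 9.4.5 pairs t-tests with rank-sum tests, which hints at what was intended, but it covers only baseline variables.

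None of this supplies a test for either primary measure.

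**Conclusion.** The point holds as a gap in specification. Sections 9.4.1 and 9.4.2 leave the primary test open to the outcome data. The t-test power in 9.2 applies only if raw means are compared. The calculation that sets enrolment is tied to no named BHB endpoint, and change in AUC has no power statement.

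Under the assumed skewed shapes at 32 per arm, power spans 0.87-0.96 (Welch), 0.31-0.97 (log scale) and 0.45-0.94 (rank-sum). The low log-scale value comes from a log analysis of a zero-origin gamma, a poor fit. These ranges rest on shapes that the documents do not give. A reader might infer that the trial is underpowered or that a switch is certain. Neither follows: both calculations in 9.2 reproduce on their own inputs, and the pilot SD makes skew plausible only for the T3 level.

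The Fisher output printed in the t-test paragraph is a definite error that does not alter enrolment. The 32 against 108 is an inconsistency unless 32 means evaluable. The plan should be changed; confidence in the practical size of the effect is medium.

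**What to change.** 1. In 9.4.2, fix the test of T3 BHB as a one-sided Welch comparison of Fast Bar and breakfast means, and the same for change in AUC. Limit the normality rule in 9.4.1 to other outcomes. Welch is proposed because it tests the mean difference that 9.2 sizes; another fixed test would also remove the data-driven choice but would need its own sizing. Keep a rank test as a sensitivity analysis. Any log-scale sensitivity analysis must keep zero readings by a stated rule; dropping those participants would select on outcome and conflict with the intention-to-treat analysis in 9.3.
2. In item 1 of 9.2, give the pooled t-test power as 0.8097 at alpha 0.05 for 31 per arm, with Welch at about 0.804 for 31 and 0.815 for 32. Keep 0.8164 and 0.0291 for Fisher only.
3. State that these powers cover BHB level and the proportion with reduced ketone, not change in AUC, and say whether that proportion is a secondary outcome.
4. Give the fasting arm as 36 enrolled (about 32 evaluable), so that the arms sum to 108.
5. State whether success needs both primary measures or either one. If either is enough with alpha split equally, restate the t-test power as about 0.72 at 32 per arm. If both are required, say that joint power is unknown because no SD for AUC is given.

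The cost is protocol wording, and enrolment need not change. The downsides are that raw means are more sensitive to outliers and that the stated power becomes slightly less favourable, or falls below 80% if alpha is split.

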1.2 SCHEMA

1.3 SCHEDULE OF ACTIVITIES (SOA)

	Screening	Day 1	Day 2				
Day		1	T0	T1	T2	T3	T4
Hours			Baseline	+1 h	+2 h	+3 h	+4 h
Example clock times			8 am	9 am	10 am	11 am	12 pm
Procedures							
Informed consent	X						
Randomization	X (1)						
Blood draw (Fingerstick)		X (morning, fasting)	X	X	X	X	X
• ketone (BHB)							
• glucose							
Intervention							
Healthy Eating Style	X (2)						
Dinner, followed by 15 h water-only fasting		X (before 5 pm)					
Breakfast Bar			X (after T0 test)				
Fast Bar™			X (after T0 test)				
Water-only fast			X	X	X	X	X
Questionnaires/ Surveys							
Demographics	X						
Contact Information	X						
Medical history							
Concomitant medications	X						
24-h dietary recall	X						
Food diary		X					
Self-evaluation			X (after T0 test)				X
Food evaluation				X			

(1) Subjects will be assigned to study arms according to the randomization scheme generated by using the web site Randomization.com (<http://www.randomization.com>).

(2) Subjects will be provided with a USDA MyPlate Plan according to his/her BMI and physical activity level (<https://www.choosemyplate.gov/resources/MyPlatePlan>) and encouraged to adopt the recommended healthy eating style for 2-3 days before starting the trial.

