9.4.5 BASELINE DESCRIPTIVE STATISTICS

Baseline comparability between randomized groups will be evaluated for demographics, age, sex, BMI. Group differences will be evaluated with t-tests or nonparametric rank sum tests for continuous variables, and chi-square tests for categorical variables. Standardized group differences (group difference divided by standard error of difference) will also be computed for each baseline variable.

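### No covariate is named for the T3 BHB comparison although T0 BHB is measured before the bar; pre-specifying it is an optional, low-cost gain in precision

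*Combined protocol and SAP*

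**What the plan says.** On the model, section 9.4.1 states: "All group comparisons on post-randomization efficacy outcomes will include randomized treatment (Fast Bar vs breakfast". That is its only statement about model terms. It also says that "normalizing transformations or nonparametric statistics will be used as needed", without saying how a baseline value would be handled under either option. Section 9.4.2 defines the primary outcome (BHB at T3, and change in BHB AUC over 0 to 4 hours) but gives no test, model or adjustment.

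On measurement, section 8.1 lists "Fingerstick for blood glucose and ketone (BHB) on baseline timepoint (before breakfast), and 1, 2, 3, and 4 hours after consuming" the bar. The Schedule of Activities (section 1.3) marks the T0 fingerstick without restriction by group and places both bars at "X (after T0 test".

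On baseline checks, section 9.4.5 says: "Baseline comparability between randomized groups will be evaluated for demographics, age, sex, BMI". BHB is not expressly named.

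On sizing, section 9.2 has two calculations. The first, "assuming ketone (BHB) levels of 0.25 (SD: 0.19) and 0.16 (SD: 0.05) mM for the Fast Bar and the Breakfast groups", is an unadjusted t test, labelled "Means: Difference between two independent means (two groups" in the software output; it needs 62 subjects. The second is a Fisher exact test assuming that "food consumption will reduce blood ketone in 67% vs. 33% of the participants in the breakfast and Fast Bar groups, respectively"; it needs 64, or 32 per arm, and so sets the size.

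**The concern.** T0 and T3 are readings of the same analyte in the same person three hours apart, so some correlation between them is plausible. To the extent that they correlate, an unadjusted T3 comparison carries between-person variation that the T0 value could remove. The T0 value is already being collected.

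Timing is the reason to settle this now. Section 9.4.6 plans a look at 50% that asks whether a relevant difference is likely, and section 9.4.1 leaves transformation and rank methods to be chosen when the data are in hand. A covariate added after that point would be open to question, so it has to be fixed beforehand if it is to be used.

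The gap is firm for T3 only. Section 9.4.2 does not say what the change in AUC is measured from, so T0 may already have a role there.

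**Working it through.** **Inputs.** From section 9.2: means 0.25 and 0.16 mM, SDs 0.19 and 0.05 mM, one-sided alpha 0.05, 36 enrolled per group with about 10% loss. 36 × 0.9 = 32.4, so 32 evaluable per arm. Two inputs are assumptions. The T0-T3 correlation r is not in the documents, so a range of 0 to 0.7 is shown. Section 9.2 also does not say that the pilot values are at T3; they are used here as if they were. Data are taken as normal on the original scale.

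**1. Reproduce the plan's figure.**
- Pooled SD = √((0.19² + 0.05²)/2) = √0.0193 = 0.1389.
- d = 0.09/0.1389 = 0.648, as stated.
- At 31 per arm the noncentrality is 0.648 × √(31/2) = 2.551, critical t is 1.671 (60 df), and power is 0.8097. This matches the plan.
- At 32 per arm the noncentrality is 2.591, critical t is 1.670 (62 df), and power is 0.821.

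**2. Add T0 as covariate (ordinary ANCOVA).** With equal T0 SDs in the two arms and one common slope, the share of T3 variance removed is:
- same r in both arms: R² = r² × (0.19 + 0.05)²/(2 × (0.19² + 0.05²)) = r² × 0.0576/0.0772 = 0.746 r²;
- correlation in the Fast Bar arm only: R² = r² × 0.0361/0.0772 = 0.468 r².

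Power uses d/√(1 − R²) with 61 df at 32 per arm. The simulations (at least 40,000 trials per setting) also include the cost of estimating the slope.

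| r | R², same r | Power, formula | Power, simulated | R², Fast Bar arm only | Power, formula | Power, simulated |
|---|---|---|---|---|---|---|
| 0 | 0 | 0.821 | 0.813 | 0 | 0.821 | 0.814 |
| 0.3 | 0.067 | 0.843 | 0.837 | 0.042 | 0.835 | 0.830 |
| 0.5 | 0.187 | 0.884 | 0.877 | 0.117 | 0.860 | 0.855 |
| 0.7 | 0.366 | 0.942 | 0.939 | 0.229 | 0.899 | 0.892 |

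The unadjusted test gave 0.82 throughout.

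**3. Break-even.** Estimating the slope inflates the variance by about 1 + 1/(64 − 4) = 1.0167. The covariate pays for itself once R² exceeds 1 − 1/1.0167 = 0.0164:
- same r: r = √(0.0164/0.746) = 0.15;
- Fast Bar arm only: r = √(0.0164/0.468) = 0.19.

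Simulation at r = 0.15 (same r) agrees: 0.820 with the covariate against 0.819 without.

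**4. Standard errors.** The SDs differ 3.8-fold (0.19/0.05), so the level was checked by simulation. With equal arms, ordinary ANCOVA rejected a true null in 0.050 to 0.054 of trials, one-sided. HC3 standard errors gave 0.045 to 0.051. HC3 ANCOVA power at r = 0, 0.3, 0.5 and 0.7 (same r) was 0.803, 0.825, 0.870 and 0.931, about 1 point below ordinary ANCOVA. Against the pooled t test, HC3 ANCOVA breaks even at r of about 0.26.

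**The case against.** The strongest reply is that nothing is broken. The unadjusted test is valid under randomization and reaches its stated power, and the only benefit rests on a correlation that the plan never gives. At r = 0.3 the gain is about 2 points with ordinary ANCOVA, and near r = 0 there is a small loss. All of this stands, and it is why the point is a suggestion rather than a defect.

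Four stronger readings are tempting, and the documents do not support them.

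- *A reader might infer that the covariate is worth naming only if r exceeds about 0.3.* That threshold comes from comparing HC3 ANCOVA with a pooled t test, so it includes the price of HC3. The covariate itself breaks even near 0.15 (same r).
- *A reader might infer that the unequal SDs make robust standard errors necessary.* Allocation is 1:1:1 (section 6.3), and with equal arms ordinary ANCOVA keeps its level. HC3 is a reasonable safeguard, for instance if dropout is uneven, but it is a choice.
- *A reader might infer that the plan would hide a T0 imbalance.* BHB is not named in section 9.4.5, but that section also computes standardized differences for its baseline variables, the Schedule of Activities labels T0 as baseline, and the AUC starts at T0. That T0 would go unshown is not established.
- *A reader might infer that a chance T0 imbalance biases the result.* At r = 0.5 in both arms, a one-standard-error imbalance moves the T3 difference by 0.5 × (0.19 + 0.05)/2 × √(2/32) = 0.015 mM, or 17% of the planned 0.09 mM. This is sampling variation that the unadjusted standard error already covers.

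One further caution stands. T0 is taken on day 2, after randomization at screening and after kits are mailed (section 6.2.1). It precedes the bar, but treating it as a baseline value assumes that assignment does not change how people fast overnight. The coded food labels in section 6.3 support that assumption; they do not prove it.

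**Conclusion.** The concern holds as an optional improvement in the T3 analysis. With 32 per arm and ordinary ANCOVA, power would move from 0.82 to about 0.84, 0.88 and 0.94 at r = 0.3, 0.5 and 0.7 if both arms correlate equally. If only the Fast Bar arm correlates, it would be about 0.83, 0.86 and 0.90 by formula, with simulation up to 1 point lower. With HC3 and the same r in both arms the figures are 0.83, 0.87 and 0.93. The downside if r is near 0 is up to about 1 point of power, or 2 with HC3.

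These sizes rest on the assumed r, on reading the pilot means and SDs as T3 values, and on normal data on the original scale. They say nothing firm about the AUC outcome. The sponsor can replace the assumed r with an estimate if its pilot data include paired T0 and T3 readings.

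**What to change.** In sections 9.4.1 and 9.4.2, before any outcome data are examined (including at the 50% interim analysis in section 9.4.6):

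- Specify ANCOVA of T3 BHB on arm (Fast Bar vs breakfast) and T0 BHB.
- State that T0 enters on the same scale if the outcome is transformed, or as a rank covariate if a rank method is used.
- State the standard-error method. Ordinary errors are adequate with equal arms; HC3 is optional at a cost of about 1 point of power.
- State the assumption that assignment does not alter the overnight fast, since T0 follows randomization and kit mailing.
- Name T0 BHB in the baseline table in section 9.4.5.

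The cost is a few lines of text and one degree of freedom. No new data are needed, and neither the sample size nor the schedule changes.
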